## **BACKGROUND AND SIGNIFICANCE**

Type 2 diabetes mellitus (T2DM) is a progressive disease and is associated with long term microvascular complications such as retinopathy, nephropathy, and neuropathy as well as cardiovascular morbidity and mortality. There is direct link between the levels of glycemia and the development of diabetes complications. Glucose lowering trials conducted in type 1 diabetes (T1D) and in new onset type 2 diabetes (T2D) patients supported the concept that improving glucose control was an effective method to reduce diabetes microvascular complications. Although individually these trials did not show statistically significant reductions in cardiovascular disease (CVD), observational follow-up of these trials suggested improved glycemic control reduces cardiovascular outcomes and may reduce mortality. In contrast intensive glycemic control for up to 6 years has at best only modestly reduced the development of CVD and renal disease in people with longstanding, inadequately controlled T2D. To achieve adequate glycemic control in patients with chronic T2D frequently requires combination of diabetes agents at increasing dosage resulting in increasing risk of side effects, including hypoglycemia, weight gain, edema and changes in blood lipid profile, that may counteract the benefactor effects of glucose lowering. Another explanation for the modest and slow benefit of glucose lowering on diabetes complication, is that chronic hyperglycemia has built up a legacy of vascular and kidney injury which is not easily or rapidly resolved. This may in part be due to increased tissue levels of advanced glycation end-products (AGEs) that formed by the non-enzymatic glycosylation of reducing sugars to amino-groups of proteins, lipoproteins or nucleic acids. Multiple clinical and epidemiological studies indicate an association between AGEs/glycoxidation products diabetes complications. We have recently demonstrated that several plasma “free” AGEs from a panel measured by LC-MS predicted long-term progression of coronary and carotid atherosclerosis in a subset of participants of the Veterans Affairs Diabetes Trial (VADT). Increases in several AGEs

also appeared to predict incident CVD events in the same VADT subset as well as in a small subcohort of the Action to Control Cardiovascular Risk in Diabetes (ACCORD).

Given the importance of chronic hyperglycemia and AGEs in the development of diabetes complications, there has been substantial interest in treatments that in addition to improving glucose control may also rapidly AGE levels. Lysulin™ is a nutraceutical tablet which contains the essential amino acid lysine, a micronutrient zinc and vitamin C as the active ingredients, together with other standard excipients (Lysulin Inc, San Diego, CA) ([www.lysulin.com](http://www.lysulin.com)). When supplemented separately, all 3 ingredients reduced blood glucose in both animal models as well as humans with T2D. The mechanisms of action appear to include improvement of both major mechanisms of T2D, insulin sensitivity and insulin secretion. Importantly, lysine also reduced AGE formation. To support the glucose-lowering efficacy of Lysulin, preliminary single-arm study in patients with T2D reported a significant, on average 10% (or 0.9 percent point) reduction in HbA1c after 12 weeks of treatment with 3.3 g daily Lysulin™. Given its minimal toxic profile due to natural character of all ingredients, the addition of Lysulin™ to current diabetes agents may improve glycemia in parallel with reducing dosage and variety of diabetes medications resulting in lower risk of side effects.

## **HYPOTHESIS**

Administration of Lysulin™ for 12 weeks will improve glycemic control in T2D patients with inadequate glycemic control. Lysulin™ may also reduce AGE levels and increase beta-cell function.

## **STUDY APPROACH**

**Trial Overview:** This will be a 3-month, randomized, placebo-controlled, double-blinded trial that tests the effects of Lysulin™ on glycemic control and AGEs levels in blood, and renal function in T2D patients, when added to the usual care for glycemic control in a standard primary care setting.

**Trial Design:** 60 patients with Type 2 DM with inadequate glycemic control will be randomly allocated in blocks for 3 months to Lysulin™ (1,110 mg TID, i.e. 3.3 g/day) or matching placebo. Fasting plasma glucose and HbA1c will be measured at baseline and then at week 6 and week 12 (visit windows at week 6 and 12 visits will be -7/+3 days). Plasma AGEs, creatinine and Cpeptide levels will be determined at baseline and at the end of the study. Lipid levels will be measured at baseline, week 6 and at the end of study.

Inclusion criteria: Age 21-75 years, Type 2 diabetes mellitus, HbA1c ≥ 7.5 % and <10.0% within 6 weeks of the screening visit treated non-pharmacologically with diet or stable doses of oral antihyperglycemic agents with or without insulin, stable body weight (< 5% change in last 3 months). Patients on insulin therapy will be on a stable dose, i.e. < 20% variation in insulin units, 6 weeks prior to the study.

Exclusion criteria: Type 1 DM, current or recent use of supplements containing lysine, zinc or vitamin C, uncontrolled hypertension (blood pressure ≥160/90 mmHg), kidney disease (serum creatinine GFR ≤50 mL/min, major illness, severe gastrointestinal disease, pregnancy, liver function tests > 2.5 times normal values in the past 3 months, currently abusing alcohol or drugs, or have a history of alcohol or drug abuse that in the investigator's opinion could cause the subject to be non-compliant; or have a general history of non-compliance with medications.

Study Visits Schedule: All visits will be performed in the Clinical Research Center (CRC) at the Phoenix VA. Completion of the entire study will involve up 3-4 visits to the CRC. After initial visit for obtaining of informed consent and screening, qualified patients will undergo a baseline testing (on the same day as screening visit or on a separate day), including blood collection for baseline measurements, and will be randomized to treatment (Lysulin™ or matching placebo). Study medication will be dispensed to the subject in a double-blinded fashion by Phoenix VA research pharmacist. Subjects will be instructed to take two tablets orally with breakfast, lunch and dinner. They will return to the CRC for clinical evaluation and blood draws after 6 and 12 weeks (final visit). Subjects will be instructed to not make major lifestyle modifications, including changes to their diet or exercise, during their study participation. At least one phone call contact will take place between interim visits to ensure medication is being taken appropriately and to help address any study related questions. At each visit a comprehensive assessment of side effects, medication compliance/competency and concurrent medical history will be obtained and entered into the database. Additional brief visits may occur as needed to ensure participant comfort/competency with treatment.

Study endpoints:

Primary: Fasting plasma glucose and HbA1c concentrations

Secondary: Fasting plasma AGEs, C-peptide concentrations and lipid measurements

Recruitment Approach: Participants will be recruited utilizing VA electronic medical records to identify potential candidates meeting inclusion criteria, as well as from the Phoenix VA primary care, specialty and women's clinics, community diabetes clinics, ads in VA newsletters and flyers,

permission to be contacted forms, on hold message, social media, clinic list, BISL, list of A1c results from lab, and through VINCI.

Diabetes care during the study: The research team will provide diet and exercise guidance at baseline and review at subsequent study visits, and monitor side effects, medication changes or general health issues of all subjects. We will notify relevant PCP providers of study activity to avoid unnecessary diabetes medication changes during the study. Addition of diabetes agents will be discouraged, but of course supported if clinically indicated. However, general and diabetes healthcare and routine lab tests will be conducted by the PCP as warranted. With hypoglycemia, excessive hyperglycemia or other adverse events - we will work with the participant and/or primary care team to evaluate/change contributory diet or behavior and/or reduce/modify other diabetes medications as appropriate.

Biochemical analyses: Plasma glucose, HbA1c, creatinine and all safety screening will be measured at the VAMC clinical laboratory using established automated methods. Plasma C-peptide levels will be measured by commercial ELISA kit in the VAMC research laboratory. AGEs will be measured by LC-MS/MS utilizing internal stable heavy isotope substituted standards (Preventage Healthcare technology) if initial data analysis indicates Lysulin had a rapid and favorable effect on HbA1c values.

Data Handling: All participants will be given non-identifying study IDs and all case report forms and samples are labeled with this information. The code for these IDs is stored in locked files in the locked office of the project manager. Only approved VA research employees will have access to study samples and data.

Statistical Analysis Plan: Univariate numerical and graphical procedures will be used to explore distributional characteristics and dependence structure of measured variables. Data transformations (e.g., logarithm) may be used to improve distributional characteristics and/or to improve linearity of relationships between response and covariates. A linear mixed effects model will be used to evaluate treatment-induced endpoints (glucose, HbA1c, AGEs, C-peptide). This approach allows the inclusion of potential covariates, and explicitly accounts for repeated measurements on each patient (and patient-to-patient variability). We will fit models to all sequential values of the response variable (including the baseline measurement), rather than computing a change score. This structure allows statistically efficient evaluation of treatment effects and allows modeling of differential treatment effects for patients with varying initial glycemic control.

Power Calculation: 54 participants will be required to complete the study to detect a 0.7% points reduction in HbA1c and 19 mg/dl reduction in fasting plasma glucose levels with 80% power at the alpha level of 0.05. This was based on SDs for HbA1c=0.9% points and fasting glucose=25 mg/dl from our previous study in patients with > 5 years duration of type 2 diabetes.

Interim analysis: Using a 2-stage group sequential trial design, an interim analysis will be performed by an independent statistician after completing first 28 participants, i.e. 14 per group. The sample size for interim analyses as well as the boundary values for the treatment effect were computed by SEQDESIGN procedure of SAS v9.4. The SEQTEST procedure will compare the test statistic with the boundary values at the interim stage so that the study can be stopped to reject or accept the null hypothesis. If the interim analysis will indicate futility, the enrollment of new patients will be discontinued. All active participants will complete the study as planned.

Ethical considerations: The study is testing a potential benefit of a diabetes supplement and is not providing a direct clinical benefit to the research subject. Participation in the study will be voluntary and won't affect standard of care. The VA has very strict research guidelines regarding clinical research. All protocols receive IRB, safety, scientific and privacy committee reviews and approval before being initiated. Audits of all studies are conducted by the compliance officer on annual basis: these include consent audits; case report form audits and other study conduct activity. All studies and their adverse events are also reviewed annually by the IRB. The study will be conducted in accordance with the Declaration of Helsinki, all local and national VA policies, and adhere to ICH GCP guidelines.

Payment Schedule: Study participants will be reimbursed \$15 for screening visit and \$25 for each completed study visit for up to \$115 for the whole study.

Reporting of Adverse Events: There is a VA policy for reporting serious adverse events, unexpected/unanticipated adverse events, and standard adverse events. Depending on the category of the event, it is reported within 5 days or annually to the IRB.

The sponsor-investigator will be responsible for reporting of all serious adverse events (SAE), unexpected/unanticipated adverse events, and standard adverse events to the appropriate authority and independent ethics committee/institutional review boards based upon federal regulations and local/IRB policies.

If the SAE or problem is UNANTICIPATED (i.e., it reflects a RISK that is NEW or GREATER than previously known) then this would be reported more rapidly and within the required local expedited

policy time frame but if the AE or problem was ANTICIPATED, this would be reported in accordance to the local policy (e.g., which may be an AE reported at continuing review).

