## **PROTOCOL SYNOPSIS**

Protocol Title:	The Effect of Lysulin on Glycemic Control and Advanced Glycation in Inadequately Controlled Type 2 Diabetes Mellitus: A Double blinded Placebo Controlled Study
Site Numbers & Names:	Phoenix VA Health Care System
Research Hypothesis:	Dietary supplement (Lysulin™) reduces blood glucose, hemoglobin A1c and Advanced Glycation Endproducts in individuals with inadequately controlled type 2 diabetes.
Study Schema: Drugs / Doses / Length of Treatment)	Lysulin 3,330 mg/d (two 555mg tablets TID) x 12 weeks
Study Objectives: 

• Primary:

• Secondary:

	The primary objective is to determine whether 12 weeks of treatment with Lysulin, compared to placebo, causes a reduction from baseline in the plasma levels of glucose, hemoglobin A1c (HbA1c) and Advanced Glycation End products (AGEs) in patients with inadequately controlled type 2 diabetes mellitus. Secondary objectives include determining whether 12 weeks of treatment with Lysulin increases beta-cell function as measured by plasma C-peptide levels.
Study Design	This is a randomized, prospective, double-blind study. Randomization to Lysulin and placebo will be in a 1:1 fashion.
Accrual Goal: (Total number of subjects)	60 subjects for the successful completion of 56 subjects
Accrual Rate: (Number of subjects expected per month)	15 subjects/month
Correlative Studies: (PK/PD, etc.)	N/A
Inclusion Criteria:	
 
1. Signed written informed consent
 
2. Able to communicate meaningfully with the investigator and legally competent to provide informed written consent
 
3. Men and women, ages 21-75 years
 
4. Diabetes, with HbA1c <math>\geq</math> 7.5 % and <math><</math> 10% within 6 weeks of screening
 
5. Stable dose of insulin (<20% change in units) 6 weeks prior to enrollment
 

Exclusion Criteria:	
1) Sex and Reproductive Status
 
 
a) Women of child-bearing potential who are unwilling or unable to use an acceptable method to avoid pregnancy for the entire study period.
 
b) Women who are pregnant or breastfeeding
 

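### Insulin use at entry is left to chance by simple blocks and is not named in the mixed model; stratifying on it and pre-specifying it is a cheap improvement

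*Combined protocol and SAP*

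**What the plan says.** - **Population.** The Inclusion criteria paragraph of the Study Approach takes patients "treated non-pharmacologically with diet or stable doses of oral antihyperglycemic agents with or without insulin". The Synopsis lists a stable insulin dose without saying that it applies only to users, but the Study Approach makes clear that insulin is optional.
- **Insulin stability.** "Patients on insulin therapy will be on a stable dose, i.e. < 20% variation in insulin units, 6 weeks prior to the study".
- **Allocation.** The Synopsis says "Randomization to Lysulin and placebo will be in a 1:1 fashion" and gives the accrual goal as "60 subjects for the successful completion of 56 subjects". The Trial Design paragraph says that patients "will be randomly allocated in blocks for 3 months". No stratification factor, minimization or block size appears anywhere.
- **Endpoints.** The primary endpoints are fasting glucose and HbA1c. The next line reads "Secondary: Fasting plasma AGEs, C-peptide concentrations and lipid measurements". C-peptide is measured only at baseline and at the end of the study.
- **Analysis.** The Statistical Analysis Plan paragraph fits a linear mixed model to all sequential values, baseline included. It says that covariates can be included and names none.
- **Interim.** A two-stage group sequential look follows the first 28 completers, 14 per group, with stopping possible to reject or accept the null hypothesis.
- **Care during the study.** Adding diabetes agents is discouraged but allowed if clinically indicated. After hypoglycemia or excessive hyperglycemia the team may "reduce/modify other diabetes medications as appropriate".

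**The concern.** Blocking equalizes the numbers per arm. It does nothing for the share of insulin users in each arm. The protocol itself treats insulin users as a distinct group, with their own eligibility rule, and one would expect them to differ from the rest in C-peptide and perhaps in how glucose, HbA1c and C-peptide move over 12 weeks. The documents give no figure for either difference.

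Two things are at stake. With about 30 per arm, and 14 per arm at the interim, a visible gap in insulin use is quite possible, and a result seen beside such a gap is open to challenge. And because no covariate is named, the decision to adjust for insulin use could be taken after the data are seen.

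**Working it through.** **1. The plan's own figure.** Normal formula, two-sided 0.05 (sidedness is not stated), 80% power, n per arm = 2(1.960 + 0.842)²(SD/difference)²:
- HbA1c: 2 × 7.849 × (0.9/0.7)² = 25.9, so 26 per arm. The t-test needs 27 per arm, or 54 in all (power 80.1%).
- Glucose: 2 × 7.849 × (25/19)² = 27.2, so 28 per arm. At 27 per arm the power is 79.7% (normal) or 78.2% (t).

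The stated 54 reproduces and is not in dispute.

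**2. Chance gap in insulin use.** With K users among 2n patients and n per arm, the number x in one arm is hypergeometric(2n, K, n). The gap is |2x − K| patients, and the SD of the difference in share is √[K(2n − K)/(2n − 1)]/n. K is an assumption throughout.

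| Look | K | SD of gap (points) | Probability of gap |
|---|---|---|---|
| Full, 30 per arm | 12 (20%) | 10.4 | ≥6 patients (20 points): 10.4% |
| | 18 (30%) | 11.9 | 15.8% |
| | 24 (40%) | 12.8 | 18.7% |
| | 30 (50%) | 13.0 | 19.6% |
| Interim, 14 per arm | 6 | 15.8 | ≥3 patients (21 points): 16.5% |
| | 8 | 17.4 | 20.9% |
| | 11 | 18.8 | 44.0% |
| | 13 | 19.2 | 44.9% |
| | 14 | 19.2 | 25.7% |

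The figures jump because the gap has the same parity as K. At full size with an odd K the gap must reach 7, and the probability is 10.3% at K = 21 and 11.9% at K = 27. At the interim an even K needs a gap of 4. The SD column is the steadier guide. At full size a gap of 30 points or more stays below 4% at every K tried. Simulated permuted blocks of 4 gave 15.6% at K = 18 and 19.6% at K = 30 for a gap of 20 points or more, so blocking alone does not help.

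**3. With stratification.** In simulated blocks of 4 within insulin strata, the largest gap was 2 of 30, or 6.7 points.

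**4. What a gap does to an unadjusted comparison.** Shift = gap in share × difference between users and non-users in outcome. Assume that difference is 0.5 SD (range 0.25 to 1.0). For a 20-point gap:
- 0.20 × 0.5 = 0.10 SD (0.05 to 0.20).
- HbA1c: 0.10 × 0.9 = 0.09 points (0.05 to 0.18), against 0.7.
- Glucose: 0.10 × 25 = 2.5 mg/dl (1.3 to 5.0), against 19.

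The standard error of an unadjusted HbA1c difference at 27 per arm is 0.9 × √(2/27) = 0.245, so 0.09 is about 0.37 of a standard error. At the interim a gap of 3 of 14 shifts HbA1c by 0.214 × 0.5 × 0.9 = 0.096, against a standard error of 0.9 × √(2/14) = 0.340, or 0.28 of a standard error. No C-peptide SD is given, so its shift can be stated only in SD units.

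**5. Cost of adjusting when a gap has occurred.** With equal arms and a 20-point gap, the squared correlation of insulin use with arm is 0.20² × 0.25/[p(1 − p)] = 0.01/[p(1 − p)]. That is 0.048 at p = 0.3 and 0.040 at p = 0.5. The variance of the treatment effect rises by 1/(1 − 0.048) = 1.05 or 1/(1 − 0.040) = 1.04, so by 4-5%.

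**The case against.** The strongest reply is that the planned analysis already does most of the work. Every endpoint in the mixed model has a baseline value, so a stable difference in level between users and non-users is in each patient's own baseline. All patients must also enter with HbA1c from 7.5% to below 10%, whatever their therapy. Chance imbalance under randomization is covered by the nominal type I error. A covariate named in advance loses only 4-5% in variance at a 20-point gap, so it does nearly as much as stratification. All of this stands.

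A reader might go further than the documents allow in three ways:
- *That the arms will be badly unbalanced.* A gap of 20 points or more is a minority event at full size.
- *That insulin use confounds the comparison.* Randomization rules out systematic bias from this source, and the sizes in the working are small against the design effects.
- *That insulin doses may change by up to 20% at entry.* The rule is a restriction on variation in the 6 weeks before the study, not a permission.

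The reply does not cover everything. Baseline values do not remove a difference in 12-week change. C-peptide has only two measurements and no power calculation. And permission to include covariates is not pre-specification.

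**Conclusion.** The point holds as a cheap design improvement, not as a flaw that threatens validity. Insulin use at entry is balanced neither by design nor by a named model term. The probabilities rest on an assumed insulin share: 30, 40 or 50% for the 16-20% at full size (10-12% at the odd counts shown), and 6 to 14 users among 28 for the 17-45% at the interim. The likely effect on HbA1c (about 0.09 points) and glucose (about 2.5 mg/dl) rests on an assumed 0.5 SD difference and is small, before the baseline value takes out its part. What remains is mainly C-peptide, whose shift cannot be sized in its own units, and an interim decision taken on 14 per arm. The sample size need not change.

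**What to change.** 1. Stratify the blocked randomization by insulin use at baseline (yes/no), one factor only, with permuted blocks within each stratum. State the block size in a document restricted from site staff.
2. Name insulin use and its interaction with visit as fixed effects in the mixed models for glucose, HbA1c, AGEs and C-peptide, and use the same terms at the interim. The interaction matters: baseline is part of the response, so a main effect alone adjusts level and leaves change untouched.
3. If randomization has begun, keep the existing scheme and pre-specify the terms before any unblinded analysis, the interim included.

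**Cost.** Two lists at the research pharmacy and no extra patients or procedures. There is one more incomplete block: with blocks of 4 the arms would usually differ by no more than 2 patients, and by at most 4. The interaction takes one degree of freedom for C-peptide and AGEs (two visits) and two for glucose and HbA1c (three visits), beyond one for the main effect.

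This does not deal with medication changes during the study. They can occur in patients on any background therapy and are a separate issue.

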
Criteria for Evaluation: Efficacy, safety, stopping rules, etc.)	Study participation will be stopped for adverse effects at the discretion of the study investigator. Subjects may stop study participation at any time and for any reason. Enrollment may be stopped due to futility or efficacy by interim analysis.
Statistical analysis:	A linear mixed effects model will be used to evaluate treatment-induced endpoints. The models will be fit for sequential values of the response variable (including the baseline measurement).
Statistical power:	54 participants will be required to complete the study to detect a of 0.7% points reduction in HbA1c and 19 mg/dl reduction in fasting plasma glucose levels with 80% power at the alpha level of 0.05. This corresponds to SDs for HbA1c 0.9% points and fasting glucose 25 mg/dl.

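### The 80% power claim at 54 completers fits a single-look HbA1c test only; it omits the two-stage design, falls slightly short for glucose, and differs from the synopsis target of 56

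*Combined protocol and SAP*

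**What the plan says.** The Study Approach, Power Calculation, states that "54 participants will be required to complete the study to detect a 0.7% points reduction in HbA1c and 19 mg/dl reduction" in fasting plasma glucose, "with 80% power at the alpha level of 0.05". It rests this on "SDs for HbA1c=0.9% points and fasting glucose=25 mg/dl from our previous study". The Statistical power row of the synopsis gives the same size and the same SDs ("54 participants will be required to complete the study to detect a of 0.7% points reduction in HbA1c"; "This corresponds to SDs for HbA1c 0.9% points and fasting glucose 25 mg/dl"). The Accrual Goal row of the synopsis gives a different number of completers: "60 subjects for the successful completion of 56 subjects".

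The next paragraph of the Study Approach, Interim analysis, adds: "Using a 2-stage group sequential trial design, an interim analysis will be performed by an independent statistician after completing first 28 participants", 14 per group. At that look the trial can stop either to reject or to accept the null. The boundaries are said to come from SAS SEQDESIGN, but their family, their values and whether futility is binding are not given. If futility is indicated, enrolment ends and participants already in the study carry on to the end. Under Study endpoints, fasting glucose and HbA1c are both primary.

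**The concern.** One number, 54, is offered as giving 80% power for two endpoints whose standardised effects differ, in a trial that is not a single-look trial. A size that just reaches 80% for the easier endpoint falls short for the harder one. At a fixed maximum size and alpha, an interim look that can end the trial either way costs some power, and the power statement does not allow for it.

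The second completer number adds to the difficulty. A reader cannot tell whether 54 or 56 marks the end of the trial, or whether the look at 28 falls at information fraction 28/54 = 0.519 or 28/56 = 0.500. Under alpha spending, that fraction affects the critical values. What is at stake is an accurate statement of power for each primary endpoint and one agreed size on which the boundary rests.

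**Working it through.** **Inputs.** From the Power Calculation paragraph: differences of 0.7 points and 19 mg/dl, SDs of 0.9 points and 25 mg/dl, alpha 0.05, 80% power, 54 completers. From the synopsis: 1:1 allocation, 60 enrolled, 56 completers, 15 subjects per month. From the Interim analysis paragraph: a look at 28 completers.

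**Assumptions.** The test is two-sided; sidedness is not stated, but a one-sided test would need only about 42 to 44 completers. The SDs apply to the between-arm comparison at week 12. Nothing is gained from the mixed model, and alpha is not split between the endpoints.

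**1. Reproducing 54 (HbA1c, single look).** d = 0.7/0.9 = 0.778. With n per arm, the noncentrality is d × √(n/2). At n = 27 it is 0.778 × √13.5 = 2.858 and the critical t on 52 df is 2.007, so power is 80.1%. At n = 26 power is 78.5%. The t-test size is therefore 27 per arm, or 54. The normal formula, n = 2(1.960 + 0.842)²/d², gives 25.9, so 26 per arm or 52. The plan's 54 is the t-test figure for HbA1c.

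**2. Glucose by the same method.** d = 19/25 = 0.760. At n = 27 the noncentrality is 2.792 and power is 78.2%. At n = 28 power is 79.8%, and at n = 29 it is 81.2%, so 80% needs 58 completers. By the normal formula, n = 27.2, so 28 per arm or 56, and power at 54 is 79.7%.

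**3. The two-stage look.** Power = P(Z1 ≥ a) + P(b < Z1 < a and Z2 ≥ c). The means of Z1 and Z2 are d√(14/2) and d√(n/2), and their correlation is √(14/n). Because a, b and c are not printed, standard families were tried. For example, O'Brien-Fleming with binding futility at n = 28 has a = 2.736, b = 0.697, c = 1.934. Each cell gives power in % by the normal calculation / with t statistics. The t figures in the two-stage rows come from 400,000 simulated trials.

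| Assumed rule | HbA1c, 54 | HbA1c, 56 | Glucose, 54 | Glucose, 56 |
|---|---|---|---|---|
| Single look | 81.5 / 80.1 | 82.9 / 81.5 | 79.7 / 78.2 | 81.2 / 79.8 |
| O'Brien-Fleming, efficacy stop only | 81.2 / 79.8 | 82.6 / 81.2 | 79.4 / 77.9 | 80.9 / 79.5 |
| O'Brien-Fleming, both stops, binding | 79.2 / 78.4 | 80.8 / 79.4 | 77.1 / 76.5 | 78.8 / 77.6 |
| O'Brien-Fleming, both stops, non-binding | 77.6 / 77.1 | 79.5 / 78.2 | 75.2 / 75.2 | 77.2 / 76.3 |
| Pocock, both stops, binding | 70.5 / 70.4 | 71.9 / 71.0 | 68.3 / 68.2 | 69.7 / 69.2 |

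The rows with both stops count a futility crossing as final.

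**4. Can the futility stop act?** At 15 per month, 60 subjects are enrolled in 60/15 = 4 months, about day 122. The 28th enrols at 28/15 = 1.87 months, about day 57, and completes 84 days later, about day 141. On the plan's own rate, enrolment is full before the look, so ending enrolment would remove nobody from the final analysis.

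**5. Where 56 may come from.** 56 = 2 × 28. An O'Brien-Fleming design with both stops, binding futility and a look at half needs 54.9 completers for HbA1c by the normal calculation. With equal arms, that rounds up to 56. This would explain both 56 and 28, but the documents do not say so.

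**The case against.** The strongest reply is that the loss from the interim look cannot be shown, because it depends on a boundary that is not printed. That stands as to size. With efficacy stopping alone under O'Brien-Fleming, HbA1c keeps 79.8% to 81.2% at 54, and at 56 the binding two-way version gives 79.4% to 80.8%. A reader might infer that the planned trial cannot have 80% power for HbA1c; the documents do not support that. The timing also stands: most of the O'Brien-Fleming loss comes from futility, which acts only if a crossing closes the question despite full enrolment. Even so, the plan does provide for stopping to accept the null, and with both stops treated as final every calculated figure at 54 is below 80%.

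A reader might also infer that glucose is seriously underpowered. It is not. The gap is under 2 points by the t-test and 0.3 by the normal formula, and the difference detectable with 80% power at 54 is 19.4 mg/dl, which rounds to the printed 19.

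The analysis is a mixed model using baseline and repeated values, not a t-test, and may recover more than is lost. If the SDs are of final values and the baseline correlation is 0.3 (both assumptions), power at 54 is 83.6% for HbA1c and 81.9% for glucose. With SDs of change, the gain is smaller. The plan claims no such gain, so it cannot support the stated figure, but it does rule out precise claims of a shortfall.

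Reading the power sentence as requiring both endpoints to be significant is tempting too. No passage requires that, so joint power is not at issue. Finally, 56 exceeds 54, so the mismatch does not itself reduce power.

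**Conclusion.** The point holds as a minor one. The document gives two completer numbers without explanation. Its 80% at 54 is a single-look, two-sided t-test figure for HbA1c (80.1%), and by the same test glucose has 78.2%. The power statement takes no account of the two-stage design described directly after it.

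The interim cost can be given only as a range. With O'Brien-Fleming-type stopping both ways, HbA1c power is 77.1% to 79.2% at 54, about 1 to 3 points under 80%, and 78.2% to 80.8% at 56. With Pocock-type rules and binding futility it is about 70% to 72%. The futility part of that cost requires a crossing to be treated as final. All of this assumes a two-sided test, an unadjusted comparison at week 12 and no alpha split. The documents do not show that the trial as a whole is inadequately sized.

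**What to change.** Use 56 completers (2 × 28) in the synopsis Accrual Goal, the synopsis Statistical power row and the Power Calculation paragraph. It lies within the 60 enrolled.

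Replace the single 80% claim with power for each primary endpoint, taken from the SEQDESIGN boundary the sponsor has already computed. State the boundary family, whether futility is binding, the sidedness of the test, and whether a futility crossing is final for the analysis. If a single-look figure is kept, give 81.5% for HbA1c and 79.8% for glucose at 56, labelled as ignoring the interim look and any gain from the mixed model. The two-stage figures above should not be written into the plan, because they rest on assumed boundaries.

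The cost is wording only. The stated power becomes slightly less favourable, and no extra patients are needed.
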